2.2 Full Analysis Set

[figure not shown]
The Full Analysis Set (FAS) will be the set of all randomized subjects who are exposed to any study lenses evaluated in this study. Each subject/eye in FAS will be analyzed according to the respective randomized lens, irrespective of the exposure.

2.3 Per Protocol Analysis Set

[figure not shown]
The Per Protocol (PP) analysis set is a subset of FAS and excludes all data which have met any of the critical deviation or evaluability criteria identified in the Deviations and Evaluability Plan (DEP). Each subject/eye in PP analysis set will be analyzed according to the respective randomized lens, irrespective of the exposure.

3 Subject Characteristics and Study Conduct Summaries

The following tables will be presented:

In addition, the following subject listings will be provided:

4 Effectiveness Analysis Strategy

This study defines one primary effectiveness endpoint, [REDACTED]

[figure not shown]
[REDACTED] The FAS will serve as the primary set for all effectiveness analyses. [REDACTED]

[figure not shown]
All data obtained in evaluable subjects/eyes will be included in the analysis. No imputation for missing values will be carried out for the effectiveness analysis.

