6.2.2 Full Analysis Set

The full analysis set (FAS) is the set of all randomized subjects who are exposed to any study lenses evaluated in this study.

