6.2.3 Per Protocol Analysis Set

The per protocol (PP) analysis set is a subset of FAS and excludes all data which have met any of the critical deviation or evaluability criteria identified in the DEP.

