6.4 Effectiveness Analyses

This study defines one primary effectiveness endpoint, [REDACTED] [REDACTED] The FAS will serve as the primary set for all effectiveness analyses. [REDACTED] [REDACTED]

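### Do the randomized-lens rule in the per-protocol set and the word evaluable distort the noninferiority comparison?

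*SAP*

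**What the plan says.** The FAS in SAP 2.2 "will be the set of all randomized subjects who are exposed to any study lenses evaluated in this study", and Protocol 6.2.2 defines it the same way. SAP 2.2 adds: "Each subject/eye in FAS will be analyzed according to the respective randomized lens, irrespective of the exposure". Protocol 6.4 and SAP section 4 both state: "The FAS will serve as the primary set for all effectiveness analyses".

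The PP set in SAP 2.3 "is a subset of FAS and excludes all data which have met any of the critical deviation or evaluability criteria identified in the" DEP. Protocol 6.2.3 has the same exclusion rule but does not say to which lens the remaining data belong. SAP 2.3 supplies that: "Each subject/eye in PP analysis set will be analyzed according to the respective randomized lens, irrespective of the exposure". Only the safety set (SAP 2.1) is grouped by the lens actually worn.

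Under missing data (Protocol 6.6), and again in SAP section 4, both documents say: "All data obtained in evaluable subjects/eyes will be included in the analysis". A no-imputation statement follows in each. Protocol 6.1 bases evaluability on the DEP and has it settled before the lens sequence is unmasked and the database locked.

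The text after the statement that FAS is primary is blacked out in both documents, as is the end of the success criterion in the SAP's executive summary. The readable text therefore does not show what part PP plays in the noninferiority decision.

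**The concern.** Two things look wrong.

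**Attribution in PP.** A per-protocol analysis is usually meant to show how the products compare when used as planned. A rule that ignores exposure matters only when the worn lens differs from the assigned one. It then books one lens's acuity under the other, which pulls the estimated difference toward zero. In a noninferiority trial that is the favourable direction. FAS has the same rule, so PP might seem to offer no check on it.

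**The word evaluable.** Evaluability comes from the DEP, and DEP criteria also define what PP removes. If the sentence in Protocol 6.6 and SAP section 4 limits the primary analysis to evaluable data, it would drop data that the FAS definition keeps. Two programmers could then build different primary datasets for the trial's only primary test.

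**Working it through.** **Step 1: what reaches the PP attribution rule.** SAP 2.3 works in order: it first removes data that meet a DEP criterion, then assigns what is left to the randomized lens. There are two cases.

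- Wrong-lens wear is a DEP criterion. Those data are gone, randomized and worn lens agree in PP, and the attribution sentence has no effect.
- Wrong-lens wear is not a DEP criterion. Those data stay and are booked under the assigned lens.

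The DEP is not among the documents, so they do not say which case applies.

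**Step 2: size in the second case.** Inputs from the documents: margin 0.05 logMAR (Protocol 6.4.1.1, SAP 4.2), one-sided 95% limit (Protocol 6.4.1.2, SAP 4.3.1), 44 completers (Protocol synopsis, SAP Table 1-1). Assumed: a standard deviation (SD) of the within-subject lens difference between 0.05 and 0.12 logMAR, because the readable text gives none; and k subjects who wore the lenses in reverse order and stayed in the set. The plan states no figure that could be reproduced first.

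Each reversed subject contributes minus the true difference, so the expected estimate is

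d = δ × (1 − 2k/44).

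With δ at the margin, 0.05: k = 1 gives 0.05 × 42/44 = 0.0477; k = 2 gives 0.05 × 40/44 = 0.0455; k = 4 gives 0.05 × 36/44 = 0.0409.

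In a paired normal approximation, the chance of declaring noninferiority when the true difference equals the margin is

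Φ((0.05 − d)/(SD/√44) − 1.645).

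For k = 1 and SD 0.05: SD/√44 = 0.00754, (0.05 − 0.0477)/0.00754 ≈ 0.30, and Φ(0.30 − 1.645) ≈ 9.0%.

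| Reversed subjects kept | Expected difference | Error, SD 0.12 | Error, SD 0.10 | Error, SD 0.08 | Error, SD 0.05 |
|---|---|---|---|---|---|
| 0 | 0.0500 | 5.0% | 5.0% | 5.0% | 5.0% |
| 1 | 0.0477 | 6.4% | 6.8% | 7.3% | 9.0% |
| 2 | 0.0455 | 8.2% | 9.0% | 10.2% | 14.9% |
| 4 | 0.0409 | 12.7% | 14.9% | 18.6% | 33.0% |

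If one subject wore the wrong lens in a single period only, d = 0.05 × 43/44 = 0.0489 and the error is 5.7% to 6.8%.

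The top row applies when nobody wears the wrong lens, and equally when such data are excluded. The lower rows need two things together: dispensing errors, and a DEP that keeps the affected data. The documents give no error rate. They do provide system-based randomization (SAP 1.3), dispensing records (Protocol 4.2) and retained lidding foils (Protocol 5.1.1 and 5.1.2). Four reversals would be 4/44 = 9.1% of completers.

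**Step 3: would analysis by worn lens be clearly better?** That is an as-treated analysis, one option among several; excluding the data is another. The primary model (SAP 4.3.1) has lens, period and sequence terms, and in a two-period crossover sequence and period together fix the assigned lens. Recoding lens alone would leave a subject with a lens that does not match the coded sequence. Someone who wore the same lens in both periods would fit neither sequence.

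**Step 4: the word evaluable.** Set side by side, the FAS definition has no evaluability condition in either document, and FAS is named as primary in both. The later sentence says that evaluable data go in; it does not say that other data come out. In the protocol it sits under missing data, and in both documents it leads into the no-imputation rule. The natural reading is that observed data are used and gaps are left unfilled. An analyst who builds the primary dataset from the set definitions gets all randomized, exposed subjects.

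**The case for a change.** The strongest reply is that evaluable has a settled meaning here. Protocol 6.1 ties it to the DEP, and PP "excludes all data which have met any of the critical deviation or evaluability criteria identified in the DEP". If the sentence in Protocol 6.6 excluded nothing, the word would do no work, and the sentence cannot be meant for PP alone because the next one speaks of the primary analysis. On attribution, if the DEP already removes wrong-lens data, the SAP 2.3 rule is redundant; if it does not, the bias favours noninferiority. Both points could be cleared up in a few words, and actual exposure is needed for the safety set anyway.

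Part of this stands. The word sits awkwardly beside the FAS definition, and the restrictive reading is possible. It is fair to ask whether wrong-lens wear counts as a critical deviation.

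It does not stand as a demonstrated fault. The restrictive reading is an inference set against an explicit definition. Evaluability is also fixed before unmasking, which limits selective exclusion even on that reading. A redundant sentence does no harm. The claims that both sets are biased and that PP gives no check depend on a DEP that is not available and on blacked-out text about PP's role.

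**Conclusion.** No change to the plan is called for. FAS follows the usual convention of analysis as randomized, and PP is defined by removing deviating data, which is what the name implies. The SAP adds detail on attribution where the protocol is silent; it does not contradict it.

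The attribution rule has no effect if nobody wears the wrong lens or if the DEP removes such data. Otherwise one reversed subject of 44 kept in PP would shrink any true difference by 2/44 = 4.5%, and raise the one-sided error at the margin from 5.0% to between 6.4% and 9.0%. Those error figures rest on assumed SDs of 0.12 down to 0.05 logMAR, a paired normal approximation and a hypothetical reversal. They show what could happen under those assumptions, not a fault in this plan.

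The evaluable sentence is loose wording that the FAS definition and its primary status let an analyst resolve sensibly. Tidier text would be harmless, but it has not been shown to alter any result or conclusion.

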4.1 Effectiveness Endpoints

Primary Endpoint

The primary endpoint is visual acuity at Dispense and Week 1, in logMAR.

4.2 Effectiveness Hypotheses

[figure not shown]
Primary Effectiveness

The null and alternative hypotheses are formulated in terms of the predefined margin of 0.05 for noninferiority:

$$H_0: \mu_{(DDT2)} - \mu_{(MYDAY)} \geq 0.05$$

$$H_a: \mu_{(DDT2)} - \mu_{(MYDAY)} < 0.05$$

where $\mu_{(DDT2)}$ and $\mu_{(MYDAY)}$ denote the mean visual acuity for DD T2 and MYDAY, respectively.

[figure not shown]

[figure not shown]
4.3 Statistical Methods for Effectiveness Analyses

4.3.1 Primary Effectiveness Analyses

A mixed effect repeated measures model will be utilized to test these hypotheses. The model will include terms for lens, visit, lens by visit interaction, period, and sequence. Within-subject correlation due to eye and crossover will also be accounted for in the model. Lens difference (DD T2 minus MYDAY) and the corresponding one-sided 95% upper confidence limit will be computed. [REDACTED]

```
proc sort data = one; by subject visit; run;  
proc mixed data = one;  
  class subject lens period sequence visit;  
  model logMAR = period sequence lens|visit /ddf=kr;  
  random int lens/subject=subject;  
  repeated visit/subject=subject*eye type=cs;  
  lsmeans lens*visit/ cl diff alpha=0.10;  
run;
```

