5 STUDY PROCEDURES AND ASSESSMENTS

5.1 Visits and Examinations

5.1.1 Visit 1 (Day 1) – Baseline/Dispense Study Lens 1

1	Explain the purpose and nature of the study, and have the subject read, sign, and date the IRB-approved informed consent document. Additionally, have the individual obtaining consent from the subject and a witness, if applicable, sign and date the informed consent document. Provide a photocopy of the signed document to the subject and place the original signed document in the subject's chart. After signing the ICF, a subject will be assigned a subject number by the EDC system. A signed informed consent document defines the point of enrollment.
2	Obtain demographic information and medical history, including information on all medications used within the past 30 days. Include herbal therapies, vitamins, and all over-the-counter as well as prescription medications.
3	[REDACTED]
4	Perform Snellen VA with habitual correction. 
• OD, OS, distance only, contact lenses*• Record habitual lens information (brand, power). *Record in Source Document only.
5	[REDACTED]
6	[REDACTED]

7	
Perform slit-lamp biomicroscopy (without contact lenses) to evaluate the following:
 
 • Limbal hyperemia • Bulbar hyperemia • Corneal staining • Conjunctival staining • Corneal vascularization • Corneal epithelial edema • Corneal stromal edema • Conjunctival compression/indention • Chemosis • Palpebral conjunctival observations • Corneal infiltrates • Other findings
8	[REDACTED]
9	Review inclusion/exclusion criteria to determine if the subject qualifies to be randomized into the study. If subject qualifies, request randomization.
10	
Based upon the randomized treatment sequence assignment, have the subject insert the appropriate study lenses.
 
 • Keep all lidding foils of lenses used during lens fit process for study lens accountability. • Follow procedures to maintain masking.
11	[REDACTED]
12	
Evaluate the study lenses by performing the following:
 
 • Snellen VA with study lenses (OD and OS, at distance)** • Over-refraction if necessary to determine the best contact lens-corrected VA and final study lens power(s) 
**VA w/study lenses must be 20/40 OU or better for subject to leave the office

13	[REDACTED]
14	[REDACTED]

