15	Assess and record any AEs and device deficiencies reported or observed during the study visit. Note: AEs and device deficiencies must be recorded for all enrolled subjects from the time of signature of informed consent including those that screen fail.
16	Dispense study lenses and instruct the subject on lens wear.
17	Schedule Visit 2 to take place 6 days (\pm 1 day) after Visit 1.

5.1.2 Visit 2 (6 Days \pm 1 Day) – Follow-up Study Lens 1 / Dispense Study Lens 2

1	Obtain information on any changes in medical health and/or the use of concomitant medications.
2	Record any device deficiencies or AEs that are observed or reported, including those associated with changes in concomitant medication dosing since the previous visit(s).
3	Review subject compliance with lens wear.
4	[REDACTED]
5	Evaluate the study lenses by performing the following: • Snellen VA with study lenses (OD and OS, at distance) Note: Perform BCVA if there is a decrease of VA by 2 lines or more with IP

[figure not shown]
6	
7	
8	Have subject remove study lenses.
9	Perform slit-lamp biomicroscopy (without contact lenses) to evaluate the following: 
• Limbal hyperemia• Bulbar hyperemia• Corneal staining• Conjunctival staining• Corneal vascularization• Corneal epithelial edema• Corneal stromal edema• Conjunctival compression/indentation• Chemosis• Palpebral conjunctival observations• Corneal infiltrates• Other findings
10	Based upon the randomized treatment sequence assignment, have the subject insert the appropriate study lenses to be evaluated. 
• Keep all lidding foils of lenses used during lens fit process for study lens accountability.• Follow procedures to maintain masking.
11	
12	Evaluate the study lenses by performing the following: 
• Snellen VA with study lenses (OD and OS, at distance)*• Over-refraction if necessary to determine the best contact lens-corrected VA and final study lens power(s) 
*VA w/study lenses must be 20/40 OU or better for subject to leave the office

13	
14	
15	Schedule Visit 3 to take place 6 days ± 1 day after Visit 2.

5.1.3 Visit 3 (6 Days ± 1 Day) - Follow-up Study Lens 2 / Exit Visit

1	Obtain information on any changes in medical health and/or the use of concomitant medications.

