6.4.1 Primary Effectiveness

The primary objective of this study is to demonstrate noninferiority in VA of DD T2 when compared to MYDAY.

The primary endpoint is VA (logMAR) at Dispense and Week 1, Follow-Up.

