6.4.1.2 Analysis Methods

A mixed effect repeated measures model will be utilized to test these hypotheses. The model will include terms for lens, visit, lens by visit interaction, period, and sequence. Within-subject correlation due to eye and the crossover will also be accounted for in the model. Lens difference (DD T2 minus MYDAY) and the corresponding one-sided 95% upper confidence limit will be computed. Noninferiority in VA will be declared if upper confidence limit is less than 0.05.

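### The primary-analysis PROC MIXED code in SAP 4.3.1 cannot fit the model in the text: `visit` does not uniquely index the four acuity records per eye, and `eye` is missing from CLASS.

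*SAP*

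**What the plan says.** SAP 4.3.1 and Protocol 6.4.1.2 describe the same primary model: fixed effects for lens, visit, lens by visit, period and sequence. On the covariance, the SAP says "Within-subject correlation due to eye and crossover will also be accounted for in the model" and the protocol says "Within-subject correlation due to eye and the crossover will also be accounted for in the model".

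The SAP then gives code. Its CLASS line is "class subject lens period sequence visit" and its repeated-measures line is "repeated visit/subject=subject*eye type=cs". A RANDOM line adds subject and subject-by-lens effects. The data are sorted by subject and visit, not by eye. Lens differences come from LSMEANS on the lens-by-visit cells.

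On the endpoint, SAP 4.1 says "The primary endpoint is visual acuity at Dispense and Week 1, in logMAR" and Protocol 6.4.1 says "The primary endpoint is VA (logMAR) at Dispense and Week 1, Follow-Up". The schedules in Protocol Table 1-1 and SAP Table 10-1 instead number visits 1 to 3, with Visit 2 labelled in Protocol 5.1 as "Follow-up Study Lens 1 / Dispense Study Lens 2". The visible text does not say which of these the variable `visit` holds.

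**The concern.** A repeated effect has to give each record within its block a distinct position. Here the block is meant to be one eye of one subject. That eye has four study-lens records, but the visit labels used in the documents supply only two or three distinct values. Records that share a value are then treated as the same measurement, and the covariance matrix becomes singular. Separately, `eye` is used to define the block but is not declared as a classification variable, so the block itself is uncertain.

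This code serves the only primary test, with its 0.05 logMAR margin, and is the only visible place where the covariance structure is written out in detail. If it stops, someone must choose a replacement once data exist. If it runs because the blocks collapse to single records, the primary confidence limit comes from a model without the eye correlation that both documents promise.

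**Working it through.** **Records per eye (Protocol 5.1).** Visit 1, step 12: one (Dispense, lens 1). Visit 2, steps 5 and 12: two (Week 1, lens 1; Dispense, lens 2). Visit 3, step 5: one (Week 1, lens 2). Each is recorded as "Snellen VA with study lenses (OD and OS, at distance". That makes 4 per eye and 8 per subject.

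**Rank with `eye` as a true block.** Compound symmetry gives R[i,j] = c + d × 1(same `visit` level), so the rank of R per eye is the number of distinct levels. The RANDOM line adds a subject effect, already in the span of the eye-by-visit indicators, and a subject-by-lens effect, which adds one dimension unless `visit` already separates the lenses. Rank of V is therefore 2 eyes × levels, plus 1 where that applies.

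| Coding of `visit` | R per eye | V per subject | Fixed-effect rank | Same-visit lens differences estimable |
|---|---|---|---|---|
| Dispense/Week 1 | 2 of 4 | 2×2+1 = 5 of 8 | 6 | 2 of 2 |
| Visit 1/2/3 | 3 of 4 | 2×3+1 = 7 of 8 | 8 | 3 of 3 |
| Four occasions | 4 of 4 | 2×4 = 8 of 8 | 8 | 0 of 4 |

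The first two are singular. In the third, period is a function of occasion, and lens within an occasion is the same as sequence. Each lens difference is therefore confounded with the sequence effect.

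Indexing by `period*visit`, with `visit` as Dispense/Week 1 and `eye` in CLASS, gives R 4 of 4, V 8 of 8, fixed-effect rank 6 (4 lens-by-visit cells + period + sequence), 2 of 2 differences estimable, and all four covariance parameters identified.

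**If `eye` is numeric and unclassed.** Assume the software opens a new block whenever the value changes from row to row. For 44 subjects there are 44 × 8 = 352 records and 88 intended blocks. With Dispense/Week 1 coding, after the sort by subject and visit, the input order yields either 176 two-record blocks, each repeating a visit level (singular again), or 352 one-record blocks. Only the second runs, and it drops the eye correlation.

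**Size in that last case.** The visible documents give no variances. Assume subject 0.004, subject-by-lens L = 0.0002, residual R = 0.004, subject-by-eye E from 0 to 0.004; n = 44, t about 1.66.

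- True per-visit SE = √[(2L + R)/n] = √(0.0044/44) = 0.0100. Visit-averaged: √[(2L + R/2)/n] = √(0.0024/44) = 0.0074.
- Without E, the within-lens stratum (6×44 − 2 = 262 df) has expected sum of squares 262R + 176E. The lens stratum (44 − 2 = 42 df) has mean square 4L + R. Once the first mean square exceeds the second, the fitted L is 0 and the fitted residual is R + (176E + 168L)/304.
- At E = 0.004: 0.004 + 0.7376/304 = 0.00643. Per-visit ratio √(0.00643/0.0044) = 1.21. Visit-averaged ratio √(0.00321/0.0024) = 1.16.
- For E = 0, 0.001, 0.002, 0.003, 0.004 the per-visit ratios are 1.00, 1.04, 1.09, 1.15, 1.21, and the visit-averaged ratios 1.00, 1.00, 1.05, 1.10, 1.16.
- Largest per-visit shift of the limit: 1.66 × 0.0100 × 0.2085 = 0.0035, or 7% of 0.05. Visit-averaged: 1.66 × 0.0074 × 0.157 = 0.0019, or 4%. One-sided alpha falls from about 5% to Φ(−1.66 × 1.2085) = 2.2%.

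**REML simulation**, complete data, 1000 replicates, E = 0.001, 0.002, 0.004: SE ratios 1.05, 1.10, 1.20; alpha without the eye correlation 3.4%, 3.1%, 2.4%, against 3.8%, 4.6%, 5.1% with the repaired code (Monte Carlo error about 0.7 points). The per-visit decision changed in at most 0.1% of trials at a true difference of 0, and in 2.9%, 5.9%, 14.1% at 0.03, a value chosen for illustration.

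**Incomplete data**, 44 complete plus 10 incomplete subjects, E = 0.001 to 0.004: the two lens estimates differ with SD at most 0.0015 logMAR (3% of the margin). With complete balanced data they are identical.

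**The case against.** A redaction sits between the prose and the code in SAP 4.3.1 and may define `visit`. That would not help: each of the three codings fails, and the CLASS and REPEATED lines are printed in full.

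A programmer would notice most of these failures at the first run, and the repair is largely dictated by the prose, the RANDOM line and the within-eye compound symmetry already named. Masking holds until database lock (Protocol 8.1), and Protocol section 6 requires deviations from the plan to go into an amendment or the study report. All of this stands and is why the point is minor. It does not make the printed code right, and more than one repair is plausible (for example, eye-by-lens blocks with a separate eye effect).

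The standard-error figures describe one row order, assumed software behaviour and assumed variances. This also stands: they are an illustration and not a bound. With assumed SDs of 0.05 (subject), 0.07 (eye), 0.01 (subject-by-lens) and 0.04 (residual), the per-visit ratio is about 1.6 and the limit moves about 0.006 logMAR, 12% of the margin.

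**Conclusion.** The concern holds, as a minor code correction. No coding of `visit` lets the printed code fit the stated model. That conclusion is algebraic and needs no variance assumption. What PROC MIXED does with an unclassed numeric `eye` is an assumption, and the effect sizes rest on assumed variances.

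The prose model is estimable and not in question, and the code's 0.10 two-sided level matches the one-sided 95% limit. Under the covariance the text promises, losing the eye correlation makes the limit too high, which is conservative: type I error is not inflated. What remains is an unplanned covariance choice for the primary test, or a modest loss of precision that nobody notices.

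**What to change.** Before unmasking, define `visit` as Dispense or Week 1 within each lens, and change two lines of the code:

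`class subject eye lens period sequence visit;`

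`repeated period*visit/subject=subject*eye type=cs;`

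The RANDOM line, the model terms and LSMEANS stay as they are. Confirm the degrees-of-freedom option as well: it prints as `ddf=kr`, which may only be a text-reading artefact. Run the program on dummy data with the planned record structure. If the two eyes are expected to share variation specific to a lens and visit, a subject-by-lens-by-visit component could be considered; it is not needed to match the text.

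The cost is two lines of code and one sentence on visit coding. No parameter is added beyond the covariance already promised, and data collection, visits and subjects are unaffected.
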